#### Methods and Systems to Ensure Data Confidentiality and Subject Privacy

The privacy and confidentiality of research participants are to be respected and protected at all times. The proposed research study will comply with the HIPAA Privacy Rule as well as all other state, federal, and institutional regulations intended to protect the rights, safety, and welfare of human participants involved in research studies. We will attempt to minimize the collection, storage, and transmission of information containing patients' personal identifiers, and, whenever identifiers are necessary, protect against unauthorized access or disclosure. In addition, we will employ several rigorous procedures for protecting against risks to participant privacy and confidentiality of data. We will only collect and store information about study participants that is relevant to the research as outlined in the protocol. All electronic data will be collected and stored on secure password-protected computers. Some paper documents, such as the consent form, will be required, and these will be stored in a locked file cabinet in a locked office of a study team member. We will establish a shared folder on a secure UNC-CH server to house all study data. This folder, as well as all study databases, will be password-protected, and only study team members who need access to these data will have permissions. Individual patient data will not be shared with individuals outside the study team, except as required by law and/or for regulatory purposes. All individuals on the study team must regularly fulfill certification requirements in Human Subjects Protection training. Study personnel are also regularly trained in stringent computer and information security procedures. All electronic study data will be securely backed up on a nightly, monthly, and biannual schedule. Monthly and biannual backups will be kept on static media throughout the duration of the study and for at least 5 years after study completion. Research study records will be

maintained for no less than 7 years following the completion of the study, after which time personal identifying information will be removed. Research information in a participant's medical record will be kept indefinitely.

#### Process for Locking Final Data

Following completion of the study, the PI will conduct a final evaluation to ensure all data has been inputted into the REDCap database. The PI, with assistance from MSU study team members will conduct a final evaluation to ensure all Fitbit data has been inputted into and stored in the SQL database. Then, the PI will notify the University REDCap Administrator to lock the REDCap study database and co-investigator to lock the SQL study database.

#### Planned Procedures for Data Access and Sharing

At the conclusion of the study, datasets will be locked for the required amount of time as outlined by the University's Institutional Review Board. At the conclusion of this period, data will be destroyed in accordance to the University's Institutional Review Board. The UNC-CH has offices responsible for ensuring privacy and confidentiality standards and safeguarding data security at the recipient site to avoid manipulation of data with the intent of identifying participants. The UNC-CH is HIPAA compliant; therefore, any datasets generated from human participants will be free of any identifiers that would allow linkages to individual participants and variables that could lead to deductive disclosure of individual participants. The final dataset will include a comprehensive group of outcome measures (demographics, injury and surgical data, physical activity data, patient-reported outcomes, and magnetic resonance imaging of knee tissues). The entire dataset will link the outcomes and demographics but will be devoid of patient identifying information. We will make our data available to other investigators that contact the PI and provide written commitment to: 1) only use the data for purposes currently unplanned by the investigators, 2) only use the data for research purposes and not to contact patients or potential future research participants, as well as 3) destroy or return raw data following completion of data analysis.

Data Request Process: Prior to authorizing data transfer the requesting PI must provide written specific aims for the study and regulatory approval from their institution for study of de-identified data. The PI of this study will decide on approving data transfer for the specific aims requested. The requestor must additionally request data use if new specific aims arise. The request process is meant to limit duplication of analyses.

Data Sharing Process: Data will be stored on a secure server at MSU. Cleaned processed and unprocessed data will be stored in its original form and using the SQL database infrastructure. We will transfer de-identified data using a secure electronic server. This process will take place in 2 weeks of the initial request unless additional data cleaning is required.

Privacy: De-identified data will always be transferred.

## 9. **RECRUITMENT STRATEGY**

We will complete the following recruitment strategies for the proposed study:

- Potential participants will be recruited verbally from classes following approval by individual course instructors. At this time, potential participants will be read a standard recruitment script detailing the inclusion criteria, procedures, duration, benefits, and potential risks associated with participation, and will be allowed to ask any questions pertaining to the investigation. All recruitment procedures will be conducted by members of the research team at the end of the specified class meetings. This will allow nonparticipating students the option of leaving the classroom, thereby alleviating pressure to participate. Individuals who are interested in participating and who meet the inclusion criteria will be provided with the PI's contact information and asked to contact the PI to address any additional questions regarding the study and to schedule data collection.
- Participants will be recruited via informational, IRB-approved flyers posted on the UNC-CH campus and in local rehabilitation clinics.
- Participants will be recruited via an informational email posted on the UNC-CH server. In the event UNC students are recruited and enrolled in the study, they will be made aware their participation is completely voluntary, and their decision to enroll in the study, or to withdraw from the study at any time will not affect their grades or status as a student. Additionally, if a UNC employee is recruited and enrolled they will be made aware their participation in the study is completely voluntary and their decision to enroll or withdraw at any time will not affect their status as an employee.
- Participants will be recruited using EPIC and physician referral from UNC Orthopedics or Campus Health (Co-investigators, [name], [name], and [name]). All subjects must receive physician approval to return to regular, unrestricted physical activity to be eligible for participation. Drs. [name], [name] and [name] will provide subjects with information regarding participation in the study following the subject's clinical visit at which this approval is obtained.
- Participants will be recruited using the Carolina Data Warehouse. We will receive a list of patients with ACL reconstruction within the past 5 years from the Carolina Data Warehouse. This patient list will include names and multiple forms of contact information that will be used to contact potential subjects via telephone, letter/US Mail, or email depending on the available contact information to determine the individual's interest in participating in the study.

## 10. CONSENT PROCESS

The screening and consenting process will be done in a private room. The study coordinator or research assistant will ask the potential participant screening questions based on the inclusion/exclusion criteria for the study. Participants will be included if they answer yes to the following questions:

- Have completed all other formal physical therapy and therapeutic exercise regimens, and will not be engaging in any other formal therapy for their ACLR during the study
- Are between the ages of 18 and 35.
- Underwent an ACLR no earlier than 6 months and no later than 5 years prior to enrollment

Participants will be excluded if they answer yes to the following questions:

- The participant underwent an ACLR revision surgery due to a previous ACL graft injury.
- Multiple ligament surgery was indicated at the time of ACLR surgery.
- A lower extremity fracture was suffered during the ACL injury.

- The participant has been diagnosed with osteoarthritis in either knee.

The study coordinator or research assistants will verbally discuss the general protocol with the patient using the consent form as a guide. They will also briefly review the purpose of the project and any potential risks of the study. The consent form will be given to the patient to read. The participant will be reminded that engagement in research is voluntary and they can stop the study at any time. All major points about the study purpose, the study protocol including the daily step promotion intervention and data collection procedures, and risks to participating in the study will be reviewed verbally between the patient and the study coordinator or research assistants. The subject will be given time to consider the study and to discuss further with the study coordinator or research assistant if desired. After all questions have been answered and the subject shows verbal understanding of the study, signatures will be obtained and the subject will be given a copy to keep. The study member will also sign the consent form as the person obtaining consent.

The PI or the Study Coordinator will be obtaining consent from subjects. The surgeons will not consent any of their own patients during the study.

## 11. PLANS FOR PUBLICATION

The investigators of this study plan to publish the results of the study as a technical note or short report in one of the following journals: Arthritis Care and Research, Journal of Athletic Training, or the Journal of Sports Rehabilitation.

## APPENDIX

### Appendix A. Extended Intervention Document

#### 5.1. INTERVENTION DOCUMENTS

##### Investigator's Brochure of Product Label/Package Insert

Not applicable to the proposed investigation.

##### Monitoring Manual

The purpose of this collaborative project is to determine if increasing daily steps will lead to increased tibiofemoral cartilage proteoglycan density following anterior cruciate ligament reconstruction (ACLR). The proposed research will be carried out at collaboratively at the University of North Carolina – Chapel Hill (UNC, PI: [name], Mentor: [name]) and Michigan State University (MSU, Co-I: [name]) which will facilitate timely recruitment and enrollment of a maximum of 12 participants from our targeted clinical population over the proposed 1-year study period. The proposed research team has experts in knee joint cartilage health after ACLR ([name]), PA measurement and promotion after ACLR ([name]), mobile intervention design and database management ([name]), biostatistics ([name]), orthopedics ([name]), and MRI ([name]) which will enable the proposed research to be executed in a scientifically rigorous manner.

##### Personnel

[name] (PI) and the members of the UNC research team, will be responsible for all participant recruitment and enrollment, data collection, data processing, and data analysis related to the proposed study. [name] will oversee all aspects of the physical activity exposure. His responsibilities will include but are not limited to management of intervention documentation, scheduling, administering the physical activity promotion exposure, monitoring fidelity of the physical activity promotion exposure, and managing potential adverse effects. Lastly, Co-I [name] will assist with technical training for the research assistants to allow them to navigate the SQL database and provide basic technical support to participants enrolled in the study. To ensure continuity between personnel administering the intervention, standard procedures (outlined below) will be followed by all personnel.

##### Description of Required Equipment

The personalized physical activity (PA) promotion will be delivered using an automated text messaging approach that has been developed and integrated into the custom SQL database environment by the study team ([name]) and a Fitbit Charge 2 PA monitor that is Bluetooth paired with the participants personal mobile device. Rationale for these selections are as follows:

- Participation in the proposed study will be limited to individuals that have access to a mobile device capable of sending and receiving text messages, downloading the most recent version of the Fitbit mobile application, and pairing a Fitbit Charge 2 PA monitor using Bluetooth. Based on our inclusion criteria, it is estimated that >95% of potential participants will have access to a device that meets these technical requirements.
- The Fitbit Charge 2 monitor is well suited for long-term monitoring based on the ease of charging, the ability to wirelessly sync data using a smartphone, ability to send, receive, and interact with text messages on the monitor display, and the ability to integrate PA monitor data into our SQL database using the Fitbit Application Programming Interface (API) in a continuous, automated manner. It is a future goal of the research team to re-develop the personalized PA promotion intervention for the full series of current generation Fitbit PA monitors, as well as monitors manufactured by other companies, in order to enable a greater number of individuals to utilize the personalized PA promotion intervention using their own preferred PA monitor.

##### Instructions for Syncing the Fitbit Charge 2 Monitor and Initializing the Run-in Period

Participants will be connected to a member of the MSU study team using a HIPAA compliant video conferencing platform (Zoom or Webex) in a quiet, private environment. The investigator or research assistant from MSU will instruct the participant to un-box the Fitbit Charge 2 monitor, access the Fitbit online portal (<https://www.fitbit.com/login>), and pair the Fitbit using a study email address + the unique participant identifier. This technique allows for multiple monitors to be associated with a single laboratory email address to prevent collection of extraneous Fitbit data or unwanted Fitbit features from being accessed by study participants. Specific directions for this process can be found below:

1. Retrieve the unique participant identifier from our SQL database through a custom-built web-based portal that will also be utilized for data entry following the enrollment study visit.
2. Access <https://www.fitbit.com/login>
3. Click "Main Menu" in options menu.
4. Choose "Set up a New Fitbit Device".
5. Choose "Existing User".
6. Enter in the Fitbit account information (email/password) you want to associate with the device.
7. For each Fitbit account append a "+Participant Identifier" to the study email address.
8. Follow the instructions to select the device and sync.
9. Access the Fitbit mobile application on the App Store and download the file.
10. Open the application and click register.
11. Complete the registration process using the participant identifier.

12. Confirm Bluetooth pairing of the Fitbit Charge 2 monitor and the Fitbit mobile application.
13. Send a test text message via the SQL database environment in order to confirm connectivity of the participants personal mobile device.
14. Confirm connectivity of the participants personal mobile device by having the participant interact with a standardized link included in the text message and check that this interaction was logged in the SQL database.
15. Fit the participant appropriately with the Fitbit Charge 2 monitor.
16. Provide the participant with the following information:
17. Participants should wear the monitor at all times unless participating in water-based sports. Any activities completed when the monitor is not being worn should be recorded in the physical activity log within the Fitbit mobile application activity log.
18. Participants should always keep the Fitbit mobile application open in the background of their mobile device. In addition, participants should interact with the application daily to ensure data syncing. If they do not sync data within a 48-hour period, they will receive a notification to do so.
19. Participants should charge the monitor when the battery level falls below 50% which is indicated on the monitor interface and in the Fitbit mobile application. If the monitor charge level falls below 50% for 3 consecutive days, they will receive a notification to charge the monitor within 24 hours.
20. If the monitor fails or they are not able to connect the monitor to their mobile device, they should contact the study team immediately for technical assistance. Contact can be made by responding to their most recent text message from the study team or via email, text, or phone call to the study team based on participant preference.
21. Guide the participant through each screen within the application and answer any questions they may have.
22. Inform the participant that activity data will be monitored by the study team over the next 10 days (run-in period) to confirm that they are compliant (following instructions) with study procedures.

#### ***Description of Instructions for Administering the Physical Activity Promotion Exposure***

Following the screening, automated, scheduled percentile-based goals will be delivered to the participant every morning via a personalized text message. The goal setting feature functions via automated processing of daily participant-level steps per day data which is used to develop a daily steps goal. Visual representation of the daily goal setting text message can be seen in Figure 1.

After screening, participants will be made aware of that the physical activity promotion period has started and a study team member will describe the specifics of the Daily Step Promotion intervention. This will include the following descriptions and instructions:

1. The participant will receive a daily text message in the morning which will include their daily step goal and a link that they will need to click to confirm receipt of the text message.
2. The link will provide access to a personalized dashboard that will display their step counts during the study period and number of days during which they achieved their step goals.
3. If they do not click the link, they will be reminded to do so later in the day via follow-up text message.
4. If they do not click the link for 2 consecutive days, they will be contacted by a study team member via phone.
5. The PA data collected by the Fitbit Charge 2 monitor will update throughout the day without any additional required effort.
6. The PA goal will change daily.
7. The participant should attempt to meet or exceed their daily PA goal.

Following this communication, the participant will complete the 8-week intervention period with minimal contact from the study team with exception of a weekly “check-in” phone call or text message, participant non-compliance, or technical difficulty. During week 6 of the study period, participants will be contacted by a study team member to schedule an appointment to complete the 8-week study visit and they will receive a reminder via text 1 week prior to the date of the visit. At the time of the 8-week study visit, a study team member will provide instructions regarding de-registration of the Fitbit Charge 2 monitor from the study account in order to re-purpose the device for personal use. The study team member will also confirm the appropriate method for delivery of study renumeration.

**Figure 1.** Example of text messages received by participants.

**Table 1:** Description of automated text messages in physical activity promotion exposure

Text Message Purpose	Text Message Scheduling	Text Message Template
Personalized PA Promotion Intervention		
Goal setting message	Frequency: daily Schedule: 8:00am EST	Good morning! Your goal is to take at least <insert personalized goal> steps today. Good Luck! Please click the link below to confirm that you have received your daily goal: <insert single use personalized link>
Motivational status update message	Frequency: daily Schedule: when the participant reaches 50% of their daily step goal.	Keep going! You are halfway to your goal of <insert personalized goal> steps today.
Goal achievement message	Frequency: daily Schedule: at the time of goal achievement	Congratulations! You have achieved your step goal for today. Keep up the great work!
Technical Support Messages		
Monitor battery charging reminder	Frequency: as needed Schedule: when battery level falls below 50% of maximum charge.	We noticed that your Fitbit battery is getting a little low. Please charge your Fitbit while you are sleeping tonight. If you are experiencing technical difficulties, please respond to this text and a study team member will contact you ASAP.
Monitor wear compliance reminder	Frequency: as needed Schedule: when an invalid <<1,000 steps>> is logged	We noticed that you may not have been wearing your Fitbit yesterday. If you forgot to do so, please make sure to wear your Fitbit today. If you are experiencing technical difficulties, please respond to this text and a study team member will contact you ASAP.

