### 1.3 Risk-Benefit Ratio

- Potential Benefits: This novel pilot study will provide essential proof-of-concept data linking mechanical loading in real-world settings with knee joint biology. The daily step promotion intervention used in this study targets step counts which are easily interpretable and can be monitored by health care professionals or the general population. We have purposefully incorporated the use of commercially available, cost-effective activity monitors and smart phones to promote accessibility when developing future randomized control trials and translation for use by patients. This study provides the first step in translating small scale observational and feasibility studies into larger randomized control trials to develop interventions that mitigate the risk of PTOA in patients after ACLR.

There is the possibility that the subject may receive no direct benefit from participation. Using a PA monitor, like a Fitbit, has the potential to enhance the amount or intensity of PA in which a person participates. While all participants may not experience an improvement in their activity participation, it is possible that participation in this study may benefit some participants individually.

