## 2 INVESTIGATIONAL PLAN (brief overview)

### 2.1 Study Design

Type of design: Single-arm pre-test post-test clinical trial

- Screening Visit: The initial visit will include initial screening (i.e. screening question and fill out KOOS-QOL subscale), enrollment, walking biomechanics assessment, and instructional use of actigraph physical activity monitor which will be worn for 7 days during all waking hours.
- Baseline: The second visit will include Fitbit and smartphone initialization with MSU Researcher, collection of patient reported outcomes and MRI scan of their knee. Participants will wear the fitbit monitor on their non-dominant wrist for 2 weeks during all waking hours in free-living settings in preparation for the intervention.
- Intervention/Treatment: Between the second and third visit, participants will receive daily SMS message with daily step count goals on their smart phone for 8 weeks. The daily step goal is based

on an adaptive step goal paradigm in which their daily goal is based on the top 60th percentile of steps over the last 10 days.

- Follow up: The third visit will include the completion of surveys, returning the fitbit monitor, instructional use of the actigraph monitor for second wear period over 7 days, and MRI.

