## 3 STUDY PROCEDURES

### 3.1 Screening Procedures

Once a potential participant has been identified and has indicated that he/she is interested in participating in the study, a study team member will then administer a screening questionnaire via telephone or in person at the orthopaedic clinic or the laboratory to further assess eligibility. We will obtain participants' verbal consent to ask a limited number of questions that include inclusion/exclusion criteria. If the individual meets self-reported screening criteria, score less than 87.5 on the KOOS quality of life subscale, and are interested in participating, participants will provide written informed consent and sign a HIPPA form at the clinic. They will be outfitted with a research-grade actigraph accelerometer to monitor daily during free-living settings for 7 days and fill out the demographic form, knee injury history form. The actigraph will be secured on a belt and placed on the right hip. Participants will be instructed to wear the device for 7 days (removed for water activity and sleep). After 7 days, participants will return to the laboratory. If participants average <8000 steps per day over the wear period then they will continue with the baseline visit.

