### 3.2 Baseline Visit Procedures

If participants average <8000 steps per day over the wear period then they will undergo an MRI at the Biomedical Imaging Research Center, complete surveys (KOOS) and be outfitted with a Fitbit Charge 2 monitor on their wrist by a researcher.

After this process is complete, participants will be connected to a member of the Michigan State University study team using a HIPAA compliant video conferencing platform. The investigator from MSU will guide the participant through monitor initialization and sync the monitor with the participant's personal mobile device. The Fitbit Versa 2 is well suited for our study design based on its ability to display SMS messages on a digital interface, ease of charging, ability to wirelessly sync data using a smartphone, and ability to continuously capture daily steps using the Fitbit Application Programming Interface (API). Monitor will be worn during all waking hours, and compliance will be considered as a day with = 1,000 steps recorded. At this visit participants will be provided a handout that describes the physical activity promotion exposure, dates of the physical activity promotion (8 weeks), and a reminder card indicating the date of their follow-up visit.

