### **3.4 Follow-up procedures**

After the intervention, participants will be outfitted at the laboratory with the research-grade actigraph accelerometer to monitor daily during free-living settings for 7 days and fill out the surveys (KOOS). The actigraph will be secured on a belt and placed on the right hip. Participants will be instructed to wear the device for 7 days (removed for water activity and sleep). Participants will also undergo another MRI of the surgical limb at the Biomedical Imaging Research Center.

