## STATISTICAL CONSIDERATIONS

#### 4.4 Primary Endpoint

- 1.) T1rho relaxation times in the medial femoral condyle at pre-intervention: MRI marker of T1rho relaxation times of medial femoral articular cartilage (i.e proteoglycan density) at pre-intervention
- 2.) T1rho relaxation times in the medial femoral condyle at post-intervention: MRI marker of T1rho relaxation times of medial femoral articular cartilage (i.e proteoglycan density) at post-intervention
- 3.) T1rho relaxation times in the lateral femoral condyle at pre-intervention: MRI marker of T1rho relaxation times of lateral femoral articular cartilage (i.e proteoglycan density) at pre-intervention
- 4.) T1rho relaxation times in the lateral femoral condyle at post-intervention: MRI marker of T1rho relaxation times of lateral femoral articular cartilage (i.e proteoglycan density) at post-intervention

- 5.) T1rho relaxation times in the medial tibial condyle at pre-intervention: MRI marker of T1rho relaxation times of medial tibial articular cartilage (i.e proteoglycan density) at pre-intervention
- 6.) T1rho relaxation times in the medial tibial condyle at post-intervention: MRI marker of T1rho relaxation times of medial tibial articular cartilage (i.e proteoglycan density) at post-intervention
- 7.) T1rho relaxation times in the lateral tibial condyle at pre-intervention: MRI marker of T1rho relaxation times of lateral tibial articular cartilage (i.e proteoglycan density) at pre-intervention
- 8.) T1rho relaxation times in the lateral tibial at post-intervention: MRI marker of T1rho relaxation times of lateral tibial articular cartilage (i.e proteoglycan density) at post-intervention
- 9.) Change in daily steps: change in average steps per day over 7 day physical activity monitor wear pre-intervention (baseline) to approximately 8-weeks (post-intervention) after physical activity promotion intervention
- 10.) Change in T1rho relaxation times in the medial femoral condyle: change in MRI marker of T1rho relaxation times of medial femoral articular cartilage (i.e proteoglycan density) from pre-intervention (baseline) to approximately 8-weeks (post-intervention) after physical activity promotion intervention

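### The plan says both that the Fitbit is returned and that it is kept at the third visit, so Fitbit wear in the post-intervention Actigraph week is undefined

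*Combined protocol and SAP*

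**What the plan says.** Three places describe the follow-up visit.

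- The synopsis (Study Phases) and section 2.1 list, for the third visit, "returning the fitbit monitor, instructional use of the actigraph monitor for second wear period over 7 days, and MRI". The Fitbit goes back at the visit where the second Actigraph period starts.
- Appendix A, in the instructions for administering the physical activity promotion, has a team member at the 8-week visit give instructions on "de-registration of the Fitbit Charge 2 monitor from the study account in order to re-purpose the device for personal use".
- Section 3.4, the follow-up procedure itself, says "After the intervention, participants will be outfitted at the laboratory with the research-grade actigraph accelerometer to monitor daily during free-living settings for 7 days". It does not say what happens to the Fitbit.

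The pre-intervention Actigraph week is the screening week. Section 3.1 puts it before the baseline visit, and section 3.2 has participants "be outfitted with a Fitbit Charge 2 monitor on their wrist by a researcher" only once they have passed the step screen.

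Section 1.3 states: "Using a PA monitor, like a Fitbit, has the potential to enhance the amount or intensity of PA in which a person participates". Section 4.4, item 9, defines the step endpoint as "change in average steps per day over 7 day physical activity monitor wear pre-intervention (baseline) to approximately 8-weeks (post-intervention", without naming the device. Section 4.1 allows either the Actigraph or the Fitbit as the source of daily steps.

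**The concern.** The two instructions concern the same visit and cannot both be followed. Under one, the participant goes through the post-intervention Actigraph week without the study Fitbit, as in the screening week. Under the other, the participant may have a step display on the wrist during the week that is meant to show what the intervention left behind.

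That week is the only planned post-intervention Actigraph measurement. It can supply the post value of a primary endpoint (change in daily steps) and one axis of the Aim 2 correlation with change in T1rho. If a Fitbit is worn in the post week only, the step change combines the intervention effect with the effect of wearing a self-monitoring device during measurement. The plan records nothing that would show afterwards which state applied. With 8 to 10 participants, there is little room to adjust for it.

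**Working it through.** **Passages side by side**

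| Question | Synopsis and 2.1 | Appendix A | 3.4 |
|---|---|---|---|
| Visit | Third visit | 8-week visit (the same visit) | Follow-up |
| Fitbit | Returned | De-registered for personal use | Not mentioned |
| Second Actigraph week | Starts here | Not mentioned | Starts here |
| Wear of a Fitbit in that week | Study device is gone | Not excluded | Not mentioned |

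Appendix A cannot be set aside as background. Sections 3.3 and 5 refer to it for the detailed procedures, and its Personnel section says all personnel follow its standard procedures.

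**What each reading implies for step change**

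Let δ be the extra steps per day from wearing a Fitbit in the post week, and p the share of participants who wear one.

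1. All returned (p = 0): no shift. The pre and post weeks match on study-Fitbit status.
2. All kept and worn (p = 1): the mean step change rises by δ. A constant added to everyone leaves a Pearson correlation unchanged.
3. Mixed (0 < p < 1): the mean rises by p × δ, and the variance of step change grows by p(1 − p)δ².

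**Illustrative size**

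The plan has no figure to reproduce here. The inputs are:

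- δ = 300 to 1,000 steps/day (assumption; no source in the documents).
- p = 0.5 for the mixed case (assumption).
- s = 1,500 to 2,500 steps/day, the SD of step change (assumption).
- r = 0.77, the correlation used in section 4.7.
- About 2,000 steps/day as a yardstick. Section 1.4 (Relevant Literature and Data) cites gains above this for adaptive goals in people at high risk of osteoarthritis. It is not a stated target of this trial.

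Mean shift:

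- p = 1: 300 to 1,000 steps/day. 300/2,000 = 15% and 1,000/2,000 = 50% of the yardstick.
- p = 0.5: 0.5 × 300 = 150, and 0.5 × 1,000 = 500 steps/day.

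Correlation in the mixed case, taking device handling as unrelated to true step change and to T1rho change: r′ = r × s / √(s² + p(1 − p)δ²).

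- δ = 300, s = 2,500: 0.77 × 2,500/√(6,250,000 + 22,500) = 0.77.
- δ = 1,000, s = 2,500: 0.77 × 2,500/√(6,250,000 + 250,000) = 0.755.
- δ = 1,000, s = 1,500: 0.77 × 1,500/√(2,250,000 + 250,000) = 0.73.
- δ = 2,000, s = 1,500 (a more extreme assumption): 0.77 × 1,500/√(2,250,000 + 1,000,000) = 0.64.

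On the 300 to 1,000 range the correlation falls only from 0.77 to about 0.73 at worst. The mean step change is the more exposed quantity.

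**The case against.** A reader might infer that the post-intervention week is in fact measured under two conditions, with some participants wearing a Fitbit and others not. The documents do not show that. Nowhere do they say that some participants return the device and others keep it. Appendix A also provides for standard procedures, standard training and weekly review of the intervention documentation, which points to one rule for everyone. Under one rule the Aim 2 correlation is untouched. This part of the objection stands.

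Keeping is also not wearing. Appendix A speaks of instructions for de-registration. It does not say that the device is set up again or worn during the Actigraph week, and the daily goal messages belong to the 8-week intervention. Section 1.3 speaks of a potential and adds that not all participants may improve. This stands too: the bias is possible but not shown.

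The step source is open. If Fitbit data supplied the post value, Fitbit status in the Actigraph week would not matter. That makes the consequence conditional, but it also shows a second gap that the same edit can close.

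T1rho is probably little affected, because the follow-up MRI is listed for the same visit, although its timing relative to the Actigraph week is not fixed. Finally, this is a pilot that stresses estimation over testing. That limits the seriousness, but a biased mean step change matters for estimation as well.

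None of this removes the contradiction. Uniform procedures cannot be relied on while the written procedures disagree.

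**Conclusion.** The contradiction is real and nothing in the documents resolves it. It leaves undefined whether participants may wear a Fitbit in the post-intervention Actigraph week, when none had a study Fitbit in the screening week. If the Actigraph week supplies the post value of endpoint 9 and a kept device is worn, the mean step change could be inflated. Noise in the Aim 2 correlation follows only if participants were handled differently, for which there is no evidence.

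The size is unknown. The 300 to 1,000 steps/day, the half-and-half split and the SD of step change are all assumptions that illustrate scale; they are not estimates. The point deserves correction because it touches a primary endpoint and costs almost nothing to settle.

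**What to change.** 1. Reconcile the synopsis and section 2.1 with Appendix A so that every participant has the same study-Fitbit status in the second Actigraph week. Preferably the Fitbit is not worn, to match the screening week. Either collect the device at the third visit or, if it is a gift, tell participants not to wear it until the Actigraph week ends. The second option needs no extra visit, which matters because the documents do not describe how the Actigraph is returned after that week.
2. State this rule in section 3.4 and in item 9 of section 4.4.
3. In item 9 and section 4.1, name the Actigraph as the step source for both the pre and post values.
4. Record for both Actigraph weeks, not only the second, whether any step-displaying device was worn. Otherwise the two weeks cannot be shown to be comparable.

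Cost: a few sentences of text, one added question per Actigraph week and, if devices are handed over later, a short delay for the participant.
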